### 5.9.3. Secondary Efficacy Endpoint Analysis

All secondary analyses have the underlying null hypothesis that there is no difference in change from Baseline in the quantity of interest between the HMTM 16 mg/day group, or the HMTM 8 mg/day group, and the control group.

The sequence of the secondary efficacy analysis is as follows:

- MRI whole brain: HMTM 16 mg/day versus control
- F-FDG-PET temporal lobe (normalized to pons): HMTM 16 mg/day versus control
- F-FDG-PET temporal lobe (normalized to pons): HMTM 8 mg/day versus control
- ADAS-cog11 and ADCS-ADL23: HMTM 8 mg/day versus control
- MRI temporoparietal lobe: HMTM 16 mg/day versus control, and HMTM 8 mg/day versus control

#### 5.9.3.1. MRI: Whole Brain Atrophy

The atrophy, defined as the absolute change from Baseline, is already calculated by the responsible imaging core laboratory (see Section 2.9.1.1). The atrophy will be analyzed using the corresponding MMRM. The estimated annualized rates and the treatment group difference are obtained from the LSM.

#### MITT population analysis

Data will be analyzed based on the MI-MITTv5 population (see Section 3.1.1) according to Section 5.9.2.1 (including the supplementary and sensitivity analysis).

In a further exploratory analysis, the Baseline values of the MRI parameters putamen, nucleus accumbens, and nucleus basalis will be included as covariates.

Sponsor:	TauRx Therapeutics Ltd.		
Protocol:	TRx-237-039		
Document Version No.:	3.0	Document Date:	07-JUN-2023

Sample SAS code with time being continuous (will be fully validated at the analysis stage):

```

PROC MIXED DATA=dataset METHOD=REML COVTEST;
  CLASS subject treatment(REF='Control') severity(REF='moderate') region(REF='Europe')
  prioruse(REF='None');

  MODEL atrophy = treatment/time severity region prioruse scorebl / SOLUTION CL
  DDFM=KENWARDROGER;

  REPEATED / SUB=subject TYPE=UN;

  LSMEANS treatment / CL;
  ESTIMATE "HMTM at Week 52" intercept 1 treatment 1 0 time 52 treatment*time 52 0 / CL;
  ESTIMATE "Control at Week 52" intercept 1 treatment 0 1 time 52 treatment*time 0 52 / CL;
  ESTIMATE "intervention effect at Week 52" treatment 1 -1 treatment*time 52 -52 / CL;
  *Polynomial time effects;
  *Quadratic;
  ESTIMATE "HMTM at Week 52 (2)" intercept 1 treatment 1 0 time 52 treatment*time 52 0
  time*time 2704 treatment*time*time 2704 0 / CL;
  ESTIMATE "Control at Week 52 (2)" intercept 1 treatment 0 1 time 52 treatment*time 0 52
  time*time 2704 treatment*time*time 0 2704 / CL;
  ESTIMATE "intervention effect at Week 52 (2)" treatment 1 -1 treatment*time 52 -52
  treatment*time*time 2704 -2704 / CL;
  *Cubic;
  ESTIMATE "HMTM at Week 52 (3)" intercept 1 treatment 1 0 time 52 treatment*time 52 0
  time*time 2704 treatment*time*time 2704 0 treatment*time*time*time 140608 0 / CL;
  ESTIMATE "Control at Week 52 (3)" intercept 1 treatment 0 1 time 52 treatment*time 0 52
  time*time 2704 treatment*time*time 0 2704 treatment*time*time*time 0 140608 / CL;
  ESTIMATE "intervention effect at Week 52 (3)" treatment 1 -1 treatment*time 52 -52
  treatment*time*time 2704 -2704 treatment*time*time*time 140608 -140608 / CL;
  RUN;

```

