#### **Sensitivity analysis to the statistical model**

Model-based sensitivity analysis are:

- Including the interaction term Baseline\*visit (scorebl/\*visit) in model statement
- Maximum likelihood (ML) (rather than REML) based repeated measures model (*method=ml*) with polynomial (linear, quadratic, and cubic) time effects and time treated as a continuous variable (number of nominal weeks as well as actual study week defined by study day divided by 7). The estimated annualized change in mean values and standard errors from Baseline to Week 52 will be presented for each treatment group. For sample SAS code see Section 5.9.3.1.

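### The per-arm Week 52 ESTIMATE rows in the SAP's continuous-time sample code leave out the baseline value and the stratification factors (and, in the cubic rows, the cubic time term), so as written they do not give the population-weighted means the plan calls for

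*SAP*

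**What the plan says.** SAP 5.9.3.1 (MRI: Whole Brain Atrophy) gives sample code with time as a continuous variable. The class list opens with "CLASS subject treatment(REF='Control') severity(REF='moderate') region(REF='Europe" and continues with prior use. The model is "MODEL atrophy = treatment/time severity region prioruse scorebl / SOLUTION CL". Baseline (`scorebl`) and time are continuous.

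The linear Week 52 rows are "intercept 1 treatment 1 0 time 52 treatment*time 52 0 / CL" for HMTM and "intercept 1 treatment 0 1 time 52 treatment*time 0 52 / CL" for control. The quadratic rows add the time-squared main term and its treatment interaction. The cubic rows end "time*time 2704 treatment*time*time 2704 0 treatment*time*time*time 140608 0 / CL" for HMTM and "time*time 2704 treatment*time*time 0 2704 treatment*time*time*time 0 140608 / CL" for control. No per-arm row has a coefficient for severity, region, prior use or baseline.

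The intended use is stated elsewhere:

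- SAP 5.9.3.1 takes the annualized rates and the group difference from least squares means. Protocol 17.4 makes these population-weighted.
- Protocol 17.4.2 uses continuous time for annualized rates, supported by contrasts with nominal time.
- For the co-primary endpoints, SAP 5.9.2.1 says of the polynomial-time sensitivity models: "The estimated annualized change in mean values and standard errors from Baseline to Week 52 will be presented for each treatment group". It refers to 5.9.3.1 for the code.

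The code is labelled as a sample to be validated at the analysis stage.

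**The concern.** An ESTIMATE row returns the linear combination that its coefficients define. A per-arm mean from a model with covariates has to say at which covariate values it is evaluated, and these rows do not. The prose asks for a mean over the study population, but the rows describe a subject with a baseline score or brain volume of zero and no stated stratum. Two things could follow. The software may decline to produce an estimate, which is visible. Or it may fill in the class effects and print a per-arm annualized change that looks plausible but belongs to baseline zero. The second is harder to notice. At stake is the per-arm descriptive output of the continuous-time models.

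**Working it through.** **1. The plan's own coefficients.** 52² = 2704 and 52³ = 140608. Both figures in the code are correct.

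**2. Target.** With observed stratum proportions p (severity), q (region) and u (prior use), and mean baseline b̄, the population-weighted Week 52 mean in the linear model is

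intercept + treatment(arm) + 52 × [time + treatment×time(arm)] + Σp·severity + Σq·region + Σu·prior use + slope × b̄.

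The rows as written stop after the time terms.

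**3. Estimability by hand.** I read the model term as treatment, time and their interaction. In the over-parameterised design, an estimable row must meet these conditions:

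- The coefficients over the levels of treatment, severity, region and prior use must each sum to the intercept coefficient.
- The treatment-by-time coefficients must sum to the time coefficient, and likewise for each higher power.

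| Row, omitted effects set to 0 | Intercept | Sum over severity levels | Cubic: sum of interactions against main term | Estimable |
|---|---|---|---|---|
| Per-arm linear or quadratic | 1 | 0 | not applicable | no |
| Per-arm cubic | 1 | 0 | 140608 against 0 | no |
| Arm difference | 0 | 0 | 140608 − 140608 = 0 against 0 | yes |

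**4. Numerical confirmation.** I built the design for 400 simulated subjects at Weeks 13, 26, 39 and 52.

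- The linear design has 1 + 2 + 1 + 2 + 3 + 2 + 2 + 1 = 14 columns and rank 9. The quadratic has 17 and rank 11. The cubic has 20 and rank 13.
- All six per-arm rows with zeros for the omitted effects: not estimable.
- Linear and quadratic rows with stratum weights added: estimable, whether or not the mean baseline is added.
- Cubic rows without the cubic main term: not estimable even with every covariate supplied, if that term is in the model. If it is not in the model, they become estimable once stratum weights are added.
- All three arm-difference rows: estimable as written.

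**5. If the class effects are filled in.** The coefficient for the continuous baseline is still 0. The row then differs from the target by −(slope × b̄), plus any difference between the filled-in stratum weights and the observed proportions.

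Neither the slope nor the mean baseline is in the documents. For illustration only, this is the shift in ADAS-cog11 units under assumed values:

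| Assumed slope per point | b̄ = 15 | b̄ = 20 | b̄ = 25 |
|---|---|---|---|
| 0.05 | −0.75 | −1.00 | −1.25 |
| 0.10 | −1.50 | −2.00 | −2.50 |
| 0.20 | −3.00 | −4.00 | −5.00 |

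The planned control decline is 6.5 units (SAP 5.3), so the range is 0.75/6.5 = 12% to 5.0/6.5 = 77%. That width shows how far the figure depends on the assumptions.

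One simulated data set (slope 0.15, baseline mean set at 20) gave 4.11 for HMTM and 7.49 for control with covariates at their means. In the reference cell at baseline 0 it gave 1.03 and 4.40. The arm difference was −3.37, the same at either setting because the covariate terms cancel.

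**6. Does another line supply the value?** The LSMEANS statement in the same block does not fix time at 52. Evaluated at mean time, complete data at nominal weeks give (13 + 26 + 39 + 52)/4 = 32.5 weeks, not 52. The nominal-visit model in SAP 5.9.2.1 does give valid per-arm Week 52 means and standard errors, but not from the continuous-time models.

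**The case against.** The best defence is that this is sample code with a promised validation step and that the governing prose is right. A programmer who works from the prose would supply the weights and the mean baseline. That makes the correction cheap, but it does not make the rows correct. They are the only code given for these outputs, and the SAP does not write down the covariate values at which they should be evaluated. SAP section 10 also places version 3.0 after the partial unblinding for the double-blind analysis, which is a reason to state those values rather than leave them to programming.

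Several limits stand:

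- A reader might infer that per-arm annualized figures cannot be obtained at all. The documents do not support that. SAP 5.9.1.4 defines the annualized rate as the absolute change from baseline at Week 52, and the nominal-visit model provides it. For the co-primary endpoints, only a model-based sensitivity analysis is touched.
- A reader might infer that the software is certain to report these rows as non-estimable. That depends on how it treats omitted class effects, which the documents do not state and which was not tested in SAS. The zero coefficient for baseline does not depend on it.
- The quadratic and cubic model statements are not printed. That the cubic main term is fitted is inferred from the quadratic rows, which do list their own main term.
- The two harms are alternatives. Where no estimate is printed, the numerical shift does not arise.

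**Conclusion.** The point holds for six per-arm rows. As written, they cannot return the population-weighted least squares mean specified by SAP 5.9.3.1 and protocol 17.4. They evaluate baseline at 0, and they are non-estimable if the omitted class effects are also 0. The two cubic rows are non-estimable in addition if the cubic main term is in the model.

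The consequence is confined to the per-arm annualized changes and standard errors from the continuous-time models, for whole-brain atrophy and for the co-primary polynomial sensitivity analysis. It would be wrong to infer any effect on the efficacy conclusions. The baseline and stratum terms cancel in the difference rows, so no treatment difference, test or success criterion changes.

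No error size can be taken from the documents. The 0.75 to 5.0 unit range rests wholly on the assumed slopes and baseline means, and nothing comparable can be given for brain volume.

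**What to change.** In SAP 5.9.3.1:

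- In all six per-arm rows, add the observed-margin weights for severity, region and prior use, and `scorebl` at its mean.
- In the two cubic per-arm rows, also add `time*time*time 140608`.
- Alternatively, replace the per-arm rows with `LSMEANS treatment / OM AT (time scorebl)=(52 <mean>)`.
- Leave the three arm-difference rows as they are.
- Print the quadratic and cubic model statements so that the rows can be checked against them.
- Check any per-arm table already produced from this code.

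The cost is a change to the SAP's code wording and a check of existing output. Design, data collection and hypotheses do not change.

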### Estimand analysis

The MRI estimand (see Section 5.9.1.4) will be estimated analogously to the primary estimand (see Sections 5.9.1.1 and 5.9.2.2).

Sponsor:	TauRx Therapeutics Ltd.		
Protocol:	TRx-237-039		
Document Version No.:	3.0	Document Date:	07-JUN-2023

### 5.9.3.2. F-FDG-PET: Temporal Lobe

If data is available from subjects with other than a CDR of 0.5, these will not be included in the analysis.

#### MITT population analysis

Data will be analyzed based on the PI-MITTv5 population (see Section 3.1.1), using an ANCOVA, including the randomization stratification variables (see Section 2.6) as fixed factors, the respective efficacy Baseline value as covariate, and the treatment indicator; with the Kenward and Roger method used for calculating the denominator degrees of freedom for the tests of fixed effects.

Sample SAS code (will be fully validated at the analysis stage):

```

PROC MIXED DATA=dataset METHOD=REML COVTEST;
  CLASS subject treatment(REF='Control') severity(REF='moderate') region(REF='Europe')
  prioruse(REF='None');
  MODEL scorediff = treatment severity region prioruse scorebl / SOLUTION CL
  DDFM=KENWARDROGER;
  LSMEANS treatment / CL;
  LSMESTIMATE treatment "intervention effect" 1 -1 / CL;
  RUN;

```

Supplementary and sensitivity analysis will be performed as described in Section 5.9.2.1, except the model-based sensitivity analysis involving the time.

#### Estimand analysis

The PET estimand (see Section 5.9.1.5) will be estimated using the ANCOVA as described previously for the MITT population.

Sample SAS code (will be fully validated at the analysis stage):

```

PROC MIXED DATA=dataset METHOD=REML COVTEST;
  CLASS subject treatment(REF='Control') severity(REF='moderate') region(REF='Europe')
  prioruse(REF='None');
  MODEL scorediff = treatment severity region prioruse scorebl / SOLUTION CL
  DDFM=KENWARDROGER;
  LSMEANS treatment / CL;
  LSMESTIMATE treatment "intervention effect" nw52 -nw52 / DIVISOR=Nhmtm CL;
  RUN;

```

Sponsor:	TauRx Therapeutics Ltd.		
Protocol:	TRx-237-039		
Document Version No.:	3.0	Document Date:	07-JUN-2023

With  $nw$  the total number of subjects who withdrew for potentially treatment-related reasons during the study until Week 52 in the respective HMTM group and  $Nhmtm$  the total sample size in the HMTM group, then  $nw52 = Nhmtm - nw$ . The numbers will need to be calculated before applying the analyses model (for example saved in macro variables).

#### **5.9.3.3. MRI: Temporoparietal Lobe Atrophy**

For this secondary variable no further sensitivity / supplementary analyses are pre-specified. If necessary, post-hoc analysis will be performed to get a more in-depth understanding of the data.

##### **MITT population analysis**

Data will be analyzed based on the MI-MITTv5 population, using the MMRM as described in the sections 5.9.2.1 and 5.9.3.1.

In an exploratory analysis the Baseline values of the MRI parameters putamen, nucleus accumbens, and nucleus basalis will be included as covariates.

##### **Estimand analysis**

Data will be analyzed according to Section 5.9.2.1 using the estimand as described in Section 5.9.1.4 adapted to the temporoparietal lobe, based on the ITTv5 population.

#### **5.9.3.4. HMTM 8 mg/day versus control**

As a general remark, for the 8 mg/day versus control comparison, the order of analysis is  $^{18}\text{F}$ -FDG-PET temporal lobe, MRI temporoparietal lobe, ADAS-cog11, ADCS-ADL23.

##### **MITT population analysis**

The analysis of ADAS-cog11 and ADCS-ADL23 will be performed as outlined in Section 5.9.2, restricted to the primary analysis models and analysis populations ITTv5 and E-MITTv5, respectively. Further post-hoc analysis may follow.

In a sensitivity analysis for E-MITTv5, all three treatment groups are included in the PROC Mixed call using appropriate contrast statements for pairwise treatment comparisons against control.

The analysis of the  $^{18}\text{F}$ -FDG-PET temporal lobe will be done as described in Section 5.9.3.2 without the sensitivity / supplementary analysis.

The analysis of the MRI temporoparietal lobe atrophy will be done as described in Section 5.9.3.3 without the MITT explorative analysis.

##### **Estimand analysis**

The analysis of ADAS-cog11 and ADCS-ADL23 will be performed as outlined in Section 5.9.2, restricted to the primary estimand, without further sensitivity analysis. Further post-hoc analysis may follow.

Sponsor:	TauRx Therapeutics Ltd.		
Protocol:	TRx-237-039		
Document Version No.:	3.0	Document Date:	07-JUN-2023

The analysis of the  $^{18}\text{F}$ -FDG-PET temporal lobe will be done as described in Section 5.9.3.2 without the sensitivity / supplementary analysis.

The analysis of the MRI temporoparietal lobe atrophy will be done as described in Section 5.9.3.3 without the MITT explorative analysis.

#### 5.9.4. Responder Analysis (Sensitivity)

This analysis is based on the ITTv5 population and is done separately for each of the five primary / secondary efficacy variables (ADAS-cog11, ADCS-ADL23, MRI whole brain, MRI temporoparietal lobe, and  $^{18}\text{F}$ -FDG-PET temporal lobe) and the exploratory efficacy variable Composite Scale, and furthermore separately for each HMTM group comparison versus control.

A responder will be defined as a subject whose change from Baseline to Week 52 is less or equal to a threshold  $T$  (if a larger value means greater impairment, otherwise: *more or equal*), which will be calculated based on the least squares means from the primary analysis model (in Section 5.9.2.1, including all three treatment groups together) and the respective MITTv5 population (E-MITTv5, MI-MITTv5, PI-MITTv5).

$T$  is defined as follows, with  $\text{LSM}_C$  and  $\text{LSM}_T$  the LSM change from Baseline at Week 52 in the control arm and (HMTM) treated arm, respectively:  $T = (\text{LSM}_C + \text{LSM}_T)/2$ .

Subjects who do not have a final assessment at Week 52 will be classified as non-responders. Subjects with no Baseline assessment will not be included in the analysis and counted as missing.

According to the study protocol, the proportion of responders will be analyzed using the Cochran-Mantel-Haenszel (CMH) test, adjusting for the randomization strata variables separately (severity, prior use of standard AD treatment, and region). In addition, the CMH test will be performed adjusting for the prior use of standard AD treatment stopped before Screening. Odds ratios and 95% confidence intervals will be presented.

Sample SAS code (will be fully validated at the analysis stage):

```

PROC LOGISTIC DATA=dataset;
  CLASS treatment(REF='Control');
  MODEL response=treatment;
  STRATA (rand)stratum;
  EXACT treatment;
  RUN;

```

As a sensitivity analysis a logistic regression will be applied to include the randomization strata variables simultaneously (without prior use of standard AD treatment stopped before Screening):

Sponsor:	TauRx Therapeutics Ltd.		
Protocol:	TRx-237-039		
Document Version No.:	3.0	Document Date:	07-JUN-2023

```
PROC LOGISTIC DATA=dataset;  
  CLASS treatment(REF='Control') severity(REF='moderate') region(REF='Europe')  
  prioruse(REF='None');
```

```
  MODEL response=treatment severity region prioruse;  
  RUN;
```

For statistically significant treatment effects (p-value < 0.05) on the aforementioned five efficacy variables, the association between responders across these variables at Week 52 will be assessed by using Pearson's chi-square test to analyze the resulting  $2 \times 2$  table. The number and percent of subjects in each cell of the  $2 \times 2$  table will be tabulated along with the p-value from the Pearson's chi-square test.

Sample SAS code (will be fully validated at the analysis stage):

```
PROC FREQ DATA=dataset;  
  TABLES response1*response2 / CHISQ;  
  RUN;
```

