### **12.3 Randomization**

Subjects will be randomized to one of three study regimens described in Section 12.2: LMTM 16 mg/day, LMTM 8 mg/day, or placebo (4:1:4, at the study level). Randomization will be stratified according to severity (three levels: MMSE 16-19, 20-25, or 26-27) at study level for those randomized to Protocol Version 5.0 and above, prior use of standard AD treatment (two levels: AChEI/memantine or none), and region (two levels: North America or Europe).

Enrollment will be such that subjects are assigned to the MMSE severity groups based on screening MMSE score with a target of approximately 2:3:1 (MMSE 16-19, MMSE 20-25, and MMSE 26-27, respectively) for those randomized to Protocol Version 5.0 and above; to achieve this target, enrollment will be monitored and controlled at the site level for high recruiting sites and capped as needed at the study level.

Randomization, stratification, and enrollment cap requirements will be controlled by a web-based RTSM system.

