#### **17.4.8 Responder Analyses**

Responder analyses will be conducted for the primary and selected secondary endpoints by dichotomizing each endpoint.

For the corresponding imaging/efficacy parameter, a responder will be defined as a subject whose change from baseline is less than or equal to a threshold “T” defined as follows (these analyses will be done separately for the LMTM 16-mg/day *versus* placebo and LMTM 8-mg/day *versus* placebo groups):

- Let LSM1 be the LSM of change from baseline for the placebo group from the respective endpoint analysis
- Let LSM2 be the LSM of change from baseline for the LMTM group from the respective endpoint analysis
- Then  $T = (LSM1 + LSM2)/2$

Thresholds will be chosen based on the E-MITT, MI-MITT, or PI-MITT population-weighted LSMs from the respective model. Subjects who do not have a final assessment will be classified as non-responders.

For each separate LMTM group comparison *versus* placebo, the proportions of responders will be compared using the Cochran-Mantel-Haenszel test, adjusting for the randomization strata. Odds ratios and 95% confidence intervals will be presented.

For each of these analyses, if there is a significant effect of treatment on an imaging as well as another imaging or clinical efficacy parameter, the association between responders across these parameters at Week 52 will be assessed by using Pearson's chi-square test to analyze the resulting  $2 \times 2$  table. The number and percent of subjects in each cell of the  $2 \times 2$  table will be tabulated along with the p-value from the Pearson's chi-square test.

Responder analyses will be used to investigate associations between various endpoints. Correlation analyses will complement or replace responder-based analyses of associations in some cases.

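### SAP 5.9.4 cites the protocol for its responder CMH test but adjusts for one factor at a time, leaving four unranked results per comparison

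*SAP*

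**What the plan says.** Protocol 17.4.8 (Responder Analyses) states that, for each LMTM dose against placebo, "the proportions of responders will be compared using the Cochran-Mantel-Haenszel test, adjusting for the randomization strata". Protocol 12.3 defines those strata by three factors: "severity (three levels: MMSE 16-19, 20-25, or 26-27"; prior use of standard AD treatment ("two levels: AChEI/memantine or none"); and "region (two levels: North America or Europe".

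SAP 5.9.4 attributes its method to the protocol, then specifies the CMH test "adjusting for the randomization strata variables separately (severity, prior use of standard AD treatment, and region". It continues: "In addition, the CMH test will be performed adjusting for the prior use of standard AD treatment stopped before Screening". Odds ratios with 95% confidence intervals are to be presented, and no version is designated as the result. The sample code is PROC LOGISTIC with an EXACT statement and one generic term, "STRATA (rand)stratum".

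The three factors enter together only in a further step: "As a sensitivity analysis a logistic regression will be applied to include the randomization strata variables simultaneously". The whole section is headed as a sensitivity analysis. SAP section 10 (Changes to Planned Analyses) does not mention the responder test.

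**The concern.** The protocol does not say that the factors are to be taken one at a time. In a stratified randomization, the strata are ordinarily the cells formed by crossing the factors. A reader of the study report who relies on the SAP's attribution would believe that the protocol's test had been run.

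The departure is also out of line with the rest of the plan. Protocol 17.4 has all models include the stratification variables unless otherwise stated. The MMRM, the PET ANCOVA and the Cox model in the SAP all carry the three factors jointly. Only the responder CMH test splits them.

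Two things are at stake. Four answers per comparison with no ranking leave the choice of headline open until the results are known. And each one-factor test ignores two of the three factors used to randomize, which costs some power if those factors predict response. SAP 5.9.4 also makes its cross-endpoint association tables depend on a significant treatment effect without naming the test. If the responder test is meant, there are four candidate triggers.

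**Working it through.** **Number of results.** Three one-factor tests plus one for prior use stopped before Screening make 3 + 1 = 4 CMH p-values per comparison, or 5 with the logistic model. SAP 5.9.4 covers six variables and both doses: 6 x 2 x 4 = 48 CMH p-values (60 with logistic). SAP 5.9.3.4 restricts the 8 mg analyses. If that removes the 8 mg responder tests altogether, 6 x 4 = 24 remain.

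**The plan's own figures.** The documents give no power for the responder test, so the check starts from SAP 5.3. With 25% withdrawal, n = 200 x 0.75 = 150 per arm, and power = Phi(d / (SD x sqrt(2/n)) - 1.96).
- ADCS-ADL23: 3.4 / (8.5 x 0.1155) = 3.464, giving 93.4% (93.2% with the t distribution). The SAP states 93.2%.
- ADAS-cog11: 2.6 / (5.9 x 0.1155) = 3.816, giving 96.8% (96.7% with t). The SAP states 96.7%.

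Both reproduce.

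**Responder rates.** The threshold is the midpoint of the two arm means, so before dropout the control rate is Phi(-d / (2 SD)) and the active rate is one minus that. For ADAS-cog11 this is Phi(-0.220) = 0.413 against 0.587; for ADCS-ADL23, Phi(-0.200) = 0.421 against 0.579. Subjects with no Week 52 value count as non-responders, so each rate is multiplied by (1 - dropout).

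**Simulation.** There were 4,000 trials per scenario, with 200 per arm (50 against 200 for 8 mg), allocation stratified on the 12 cells, severity mix 2:3:1 (SAP 2.6), and 22.5% missing (midpoint of 20-25%). In stratum k, with n subjects, n1 active, n0 control, m1 responders, m0 non-responders and a active responders, the statistic is (sum a - sum n1 m1/n)^2 / sum[n1 n0 m1 m0 / (n^2 (n-1))], compared with chi-square on 1 df.

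Assumptions not in the documents: prior use and region each split 50:50; 60% of prior users stopped before Screening; and factor effects of none, moderate (0.4 SD per severity step, 0.3 SD for each other factor) or strong (0.8 and 0.6 SD).

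| Comparison | Factor effect | 12 strata, power % | Four SAP versions, power % | Difference, points |
|---|---|---|---|---|
| ADAS-cog11, 16 mg | none | 79.8 | 79.6-79.9 | -0.1 to 0.2 |
| | moderate | 76.2 | 75.0-75.8 | 0.4 to 1.2 |
| | strong | 67.6 | 62.4-65.5 | 2.1 to 5.2 |
| ADCS-ADL23, 16 mg | none | 70.4 | 70.4-70.6 | -0.2 to 0.0 |
| | moderate | 68.0 | 66.7-67.5 | 0.5 to 1.3 |
| | strong | 60.7 | 54.7-58.4 | 2.3 to 6.0 |
| ADAS-cog11, 8 mg | none | 43.6 | 43.8-43.9 | -0.3 to -0.2 |
| | moderate | 40.3 | 39.1-39.8 | 0.5 to 1.2 |
| | strong | 35.6 | 30.4-33.6 | 2.0 to 5.2 |

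**Type I error** (ADAS-cog11 inputs, no treatment effect; Monte Carlo standard error sqrt(0.05 x 0.95 / 4000) = 0.34 points). For none, moderate and strong factor effects, the 12-stratum test rejects in 5.4%, 5.7% and 5.2% of trials. The single versions reject in 5.3-5.4%, 5.2-5.5% and 3.8-4.4%. At least one of the four rejects in 5.6%, 5.7% and 4.7%.

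**Disagreement** = P(any of the four significant) - P(all four). For 16 mg with a real effect:
- ADAS-cog11: 80.2 - 79.2 = 1.0, 76.7 - 74.3 = 2.4 and 66.2 - 61.6 = 4.6 points.
- ADCS-ADL23: 71.0 - 69.9 = 1.1, 68.2 - 66.0 = 2.2 and 59.1 - 53.4 = 5.7 points.

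**Sparse case.** The 8 mg PET comparison uses only CDR 0.5 subjects. Assuming 20 against 80, about 2.7 to 4.4 of the 100 subjects fall in cells with one arm only and drop out. The 12-stratum test then loses about half a point to 1 point when the factors have no effect, and gains when they are strong.

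**The case against.** The case for leaving the section alone is fair in several respects. It is a sensitivity analysis; superiority rests on the two co-primary MMRM tests. The protocol leaves detail to the SAP. A joint adjustment is already planned through the logistic model. All of that stands and limits the weight of the point. It does not make the attribution to the protocol correct or say which result leads.

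Several stronger readings are tempting and are not supported:
- *Four tests inflate the false-positive rate.* Four independent tests would give 1 - 0.95^4 = 18.5%, but these reuse the same outcomes. The simulated chance that any is significant under the null is 4.7 to 5.7%, no higher than the single test to within simulation error.
- *The SAP's test is less powerful, full stop.* The documents give no prognostic strength for any factor. With none there is no loss.
- *The sample code is not a CMH test and is therefore wrong.* With a binary treatment, the conditional score statistic of a stratified logistic model is the Mantel-Haenszel statistic (a numerical check gave 3.3489 for both), and the exact version is its counterpart. The generic stratum term could even mean the combined stratum. The code is ambiguous, and the SAP says it will be validated later.
- *The split was chosen after seeing results.* SAP v3.0 postdates the partial unblinding, but its modification history does not mention the responder analysis, so nothing shows when the wording arose.

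One objection shapes the remedy: deleting planned versions now, after unblinding, would itself be a selection.

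**Conclusion.** The point holds as a reporting defect of modest size. SAP 5.9.4 credits the protocol with an adjustment that the protocol does not describe, produces four CMH results per comparison without a lead, and leaves the change out of section 10. The harm is room to choose among answers that differ on significance in about 1 to 6% of trials with a real 16 mg effect.

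The power cost is conditional: about 0, 1 and 2 to 6 points for no, moderate and strong factor effects, with the one-factor tests slightly conservative only in the strong case. Those figures rest on the SAP 5.3 effect sizes and SDs, 22.5% missing as non-responders, and the assumed factor splits and strengths. Type I error and the co-primary conclusion are not affected.

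**What to change.** In SAP 5.9.4:
- Name one CMH test per comparison, over the 3 x 2 x 2 = 12 combined randomization strata, as the lead responder result, with its common odds ratio and 95% CI.
- State a sparse-cell rule. For example, pool strata for the small 8 mg PET comparison, collapsing region first and then prior use, in line with the removal order that SAP 5.9.2.1 already gives for models that do not converge.
- Make the sample code show the combined stratum explicitly.
- Keep the joint logistic model, the one-factor versions and the prior-use-stopped version, all labelled supportive.
- Correct the attribution to the protocol, and record the change in SAP section 10 as made after the double-blind unblinding.

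The cost is a few lines of text and code. The only statistical price is about half a point to 1 point of power in very sparse comparisons when the factors are not prognostic.
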